#### Exclusion Criteria:

Subjects will be excluded from the trial if any of the following exclusion criteria apply prior to enrollment:

- 1. History of hypersensitivity to
- 2. History of alcohol abuse or use of recreational drugs within 12 months prior to Visit 1
- 3. History of chronic use of concomitant medications in neurologic or psychiatric illness which would affect the assessment of the safety of the trial medication
- 4. If the investigator feels that participation in this study is not in the best interest of the subject

Investigational product, dosage and mode of administration, and batch number:			

Subjects enrolled following the completion of protocol CLR\_09\_21 will receive as follows:

- Subjects who were randomized to study CLR\_09\_21 (Part 3) will continue to receive the same dose of as they received in study CLR\_09\_21.
- Subjects who were randomized to in the double-blind part of study CLR\_09\_21 (Part 3), will receive the dose of that they received in open-label fixed dose phase (Part 2) of study CLR\_09\_21.

Subjects enrolled in this study who participated in the double-blind phase of study CLR\_09\_21 will temporarily receive blinded study medication in the first 4 weeks dispensed according to the IVRS/IWRS.

**Duration of treatment:** Subjects will continue to receive treatment for the length of the trial.

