3.2.3 Study Assessments Schedules

Study assessments are described in detail in the protocol, and summarized below in Table 1.

Table 1: Visits and Procedures Schedule

	Day -14	Day 1	Day 28	Day 84	Day 182	
Activities	Week -2 Visit 1 (Screen)	Week 1 Visit 2 (Baseline)	Week 4 ± 5 days Visit 3	Week 12 ± 5 days Visit 4	Week 26 ± 5 Days Visit 5 / Premature Termination Visit ^b	Visits Every 3 Months ± 5 days ^c
Informed consent	X	-	-	-	-	
Medical history and demographics	Х	-	-	-	-	
Physical examination	X	-	-	-	X	
Neurologic examination	X	-	-	-	X	
Urine pregnancy test	X	-	X	X	X	X
Vital signs (sitting)	X	-	X	X	X	
Clinical laboratory tests ^d	X	-	-	-	X	
12-lead ECG ^e	X	-	X	X	Xe	
C-SSRS	Xf	-	X	X	X	X
Concomitant medication and physical therapy assessments	X	X	X	X	Х	X
AE evaluation	Xs	Χs	X	X	X	X
Dispense study medication	Xh	X	X	X	X	X
Collect study medication	-	X ⁱ	X	X	X	X
Dispense / collect subject diaries	Xj	Х	X	Х	Х	X
Schedule next visit	X	X	X	X	X	X

^{*}Screening Visit assessments in CLR_11_04 which are identical to final visit assessments in CLR_09_21 do not need to be repeated. The Screening Visit may be completed simultaneously with the final visit for CLR_09_21, and on the following day, if needed, provided drug supply from CLR_09_21 does not run out. Subjects cannot enter CLR_11_04 if drug supply runs out prior to the completion of the screening process.

SAEs recorded for subjects entering from clinical trial CLR 09 21only

For subjects not completing the study, all activities scheduled at this visit are to be conducted during the Premature Termination visit with the exception of the ECG (see footnote "e" below) and the physical and neurologic examinations. These three assessments may be conducted during the Premature Termination visit as needed in order to follow the

Hematology: red blood cell (RBC) count, hemoglobin, total white blood cell (WBC) count, differential WBC count, platelet count; serum chemistry: sodium, potassium, chloride, blood urea nitrogen (BUN), creatinine.

^{*}Completed in triplicate two minute intervals during Visit 5. 12-lead ECG should be performed at the Premature Termination visit, as needed, in order to follow adverse events to resolution

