4.2 Study Definitions

4.2.1 Study Day

For purposes of describing days on study drug in data listings, data will be assigned a study day, relative to the start of study drug at either Visit 1 or Visit 2, depending on whether they are roll-over subjects or non roll-over subjects. The following rules will be used (this numbering of days differs from the Study Days as described in the protocol):

Roll-over Subjects

For events that occurred after the Visit 1:

Study Day = visit date - date of Visit 1 + 1

For events occurred before study drug administration:

Study Day = visit date - date of Visit 1

Non Roll-over Subjects

For events that occurred after the Visit 2:

Study Day = visit date - date of Visit 2 + 1

For events occurred before study drug administration:

Study Day = visit date - date of Visit 2

Visit numbers as designated on the study eCRFs (Electronic Case Report Forms) will be used. For selected parameters, visit windows will also be calculated for use in descriptive statistics by time.

Version 1.0

30Oct2017

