Glucose (random)	≤ 2.775 or ≥ 9.99 mmol/L	≤ 50 or ≥ 180 mg/dL			
BUN	≥ 30 mg/dL	> 30 mg/dL			
Creatinine	≥ 176.8 µmol/L	≥ 2.0 mg/dL			
Calcium, plasma	≤ 1.75 or ≥ 3.875 mmol/L	≤ 7 or ≥ 15.5 mg/dL			
ALT / SGPT	≥ 3 × ULN	≥ 3 × ULN			
AST / SGOT	≥ 3 × ULN	≥ 3 × ULN			
Alkaline phosphatase (ALK-P)	≥ 3 ×ULN	≥ 3 × ULN			
Total bilirubin	≥ 34.2 µmol/L	≥ 2.0 mg/dL			
Total protein	≤ 45 or ≥ 90 g/L	≤ 4.5 or ≥ 9.0 g/dL			
Albumin	≤ 25 or ≥ 65 g/L	$\leq 2.5 \text{ or } \geq 6.5 \text{ g/dL}$			
Creatinine clearance	< 70 mL/min	< 70 mL/min			

S.I. = International System of Units; ULN = upper limit of the [normal] reference range Medium = serum, unless otherwise noted

The number and percentage of subjects with a PCS post-baseline laboratory value over all visits will be tabulated. Subjects with baseline and at least one post-baseline assessment will be included in the denominator and subjects who meet the PCS criteria at least once (based on all post-baseline assessments including unscheduled visits) will be included in the numerator. Subjects with a PCS post-baseline value will be flagged in laboratory listings.

Clinical laboratory results will be listed for all subjects, inclusive of flags for whether or not the value is outside the laboratory normal range, considered significant by the investigator, or met the pre-specified criteria for being possibly clinically significant.

6.3.4 **12-Lead ECG**

ECGs will be assessed at visit 1 (screening), visit 3 (week 4), visit 4 (week 12), and visit 5 (week 26). ECG measurements will be collected in triplicate 2 minues apart and read at the investigator site. The following intervals will be collected: HR, PR, RR, QRS, QT, and QTc. The QTc interval will be presented by both the Bazett (QTcB = QT/(RR)^{1/2}) and the Fridericia (QTcF = QT/(RR)^{1/2}) corrections. For QTcF and QTcB at each study visit, the distribution of

maximum values (≤ 450 , $>450 - \le 480$, >450 males, >470 females, $>480 - \le 500$, and >

500 msec) as well as the distribution of the greatest change from visit 1 (0 or less [no increase], 1-29 msec, 30-60 msec, > 60 msec, and > 60 msec increase or > 500 msec) will be presented. Appropriate visit windows for categorizing results will be established prior to database lock and unblinding. When more than one value is available within a given visit window, the latest value will be used for tabulation purposes.

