For the purposes of summary and analysis, results from the triplicate measurements at each visit will be averaged. ECG results will be summarized by visit using counts and percentages for abnormalities noted by the investigator and T-wave abnormalities, and using descriptive statistics (n, mean, standard deviation, minimum, median, maximum, and 95% CI) for interval data. For abnormality designations collected in triplicate, the worst outcome will be selected in the following order: Abnormal, Clinically Significant>Abnormal, Clinically Non-Significant>Normal. Any ECG abnormalities, based on clinical interpretation, will be reviewed for any emergent abnormalities that could be attributed to the new dosage form. Continuous ECG parameters will be summarized as change from Baseline (visit 1). For the summary of change statistics, the Baseline mean and standard deviation will be provided for the subset of subjects with available data for the change summary.

ECG results, including clinical interpretation and a flag for whether or not the value meets criteria for being possibly clinically significant, will be listed for all subjects.

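### SAP 6.3.4 asks for maximum QTc and greatest change at each visit, but its latest-value rule has no exception for these tables and can drop a higher earlier ECG

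*SAP*

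**What the plan says.** SAP 6.3.4 (12-Lead ECG) specifies two categorical displays. The first is introduced by "For QTcF and QTcB at each study visit, the distribution of" and covers maximum values, in bands running from 450 ms or less to above 500 ms. The second is "the distribution of the greatest change from visit 1 (0 or less [no increase], 1-29 msec, 30-60 msec", with further categories above 60 ms. The same paragraph then says: "Appropriate visit windows for categorizing results will be established prior to database lock and unblinding". It closes with "When more than one value is available within a given visit window, the latest value will be used for tabulation purposes".

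The next paragraph of 6.3.4 says that "results from the triplicate measurements at each visit will be averaged" for summary and analysis. It names one exception: for the investigator's abnormality rating, the worst of the three is kept.

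Three other places bear on this:

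- SAP 4.2.1 gives the purpose of windows: "For selected parameters, visit windows will also be calculated for use in descriptive statistics by time".
- SAP 6.3.2 and 6.3.3 count a subject in the overall table of possibly clinically significant (PCS) values if any post-baseline assessment qualifies, unscheduled visits included. The planned PCS tables (14.3.4.1.2, 14.3.4.2.3, 14.3.4.3.3) are titled as by visit and overall. The title of the ECG table (14.3.4.4) mentions no overall count.
- ECGs are scheduled at Visits 1, 3, 4 and 5 only. The schedule has one column headed "Visit 5 / Premature Termination Visit". At premature termination an ECG is done only as needed, to follow adverse events until they resolve (Protocol 10.5 and Table 1 footnotes). Protocol 10.6 and 10.7 list no ECG for the three-monthly or unscheduled visits.

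**The concern.** A table of maximum QTc and greatest change exists to show each subject's worst value. A rule that keeps only the last value in a window works against that purpose. The windows are described as being for categorizing results, so the rule plainly reaches these categorical tables, and nothing exempts them.

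The error has one direction. A repeat ECG is often taken because an earlier one looked abnormal, and a termination ECG is taken to see an adverse event settle. If the later session falls in the same window, the recovered value replaces the high one in the count. These tables are the SAP's only numerical threshold summary of QTc. The SAP text specifies no any-time QTc count from which a dropped value could be recovered.

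**Working it through.** The plan has no figure to reproduce here. The check is one of logic, followed by a rough size.

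**Step 1: the rules applied in order.** Let a window hold k ECG sessions with triplicate means m1, ..., mk in time order, and let B be the Visit 1 value.

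- Averaging leaves m1, ..., mk.
- The latest-value rule tabulates T = mk.
- The table title asks for M = max(m1, ..., mk), or M − B for change.

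If k = 1, T = M and the word maximum does nothing. If k ≥ 2, T ≤ M and T − B ≤ M − B. The number of subjects above any cut is therefore the same or lower under the rule, never higher.

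**Step 2: an invented example.** Suppose one window holds readings 486, 484, 482 and later 446, 448, 444.

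- Session means: 1452/3 = 484 and 1338/3 = 446.
- Highest session mean: 484, in the band above 480 and up to 500 ms.
- Value tabulated under the rule: 446, in the band 450 ms or less.

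**Step 3: how many subjects could have two sessions.** The documents do not say. For illustration, assume that a termination ECG after Week 26 is assigned to the Week 26 window.

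- If the targets are met exactly, subjects past 26 weeks but short of one year number 250 − 200 = 50 (Protocol Synopsis, trial period; SAP 3.2.1) or 250 − 100 = 150 (Protocol 7.1, 12.1). Some of these would still be on treatment. Terminations after one year would add to them.
- Assume 10% to 30% of them have a termination ECG: 0.10 × 50 = 5 up to 0.30 × 150 = 45 subjects.

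**Step 4: chance that the rule hides a value above 450 ms.** All inputs are assumed: mean 405, 415 or 425 ms; between-subject SD 15 or 18; between-session SD 5, 8 or 12; single-reading SD 4, 6 or 8; termination unrelated to QTc. That gives 3 × 2 × 3 × 3 = 54 scenarios.

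- Variance of a session mean: V = SDsubject² + SDsession² + SDreading²/3
- Correlation of two sessions: ρ = SDsubject²/V
- z = (450 − mean)/√V
- P(loss) = P(Z1 > z) − P(Z1 > z and Z2 > z), with Z1, Z2 bivariate normal with correlation ρ

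One scenario in full (415; 18; 8; 6): V = 324 + 64 + 12 = 400, ρ = 324/400 = 0.81, z = 35/20 = 1.75. P(Z1 > z) = 0.0401, both above = 0.0196, P(loss) = 0.0205. Expected loss is 5 × 0.0205 = 0.10 to 45 × 0.0205 = 0.92 subjects.

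Over the 54 scenarios, at the 450 ms cut:

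| | Minimum | Median | Maximum |
|---|---|---|---|
| P(loss) | 0.0014 | 0.0173 | 0.0684 |
| Expected loss, 5 subjects | 0.007 | 0.09 | 0.34 |
| Expected loss, 45 subjects | 0.06 | 0.8 | 3.1 |

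With 45 subjects, 30 of the 54 scenarios give less than one subject; with 5 subjects, all do. At the higher cuts the worst scenario with 45 subjects loses 0.23 subjects above 480 ms and 0.014 above 500 ms. If no window holds two sessions, the loss is 0.

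These figures are not an upper bound. An ECG taken to follow a QTc-related event to resolution would tend to be lower than the earlier one, which the calculation does not model.

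**The case against.** The strongest reply is that little is left open in practice, and much of it stands.

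- **Averaging.** A reader might infer that maximum could mean the highest single reading, so that counts are ambiguous for every subject at every visit. The SAP does not support this. Its averaging rule is general and has one named exception, which is not QTc. On its face the tabulated value is a triplicate mean. Likewise, the Visit 1 value follows from that rule and SAP 4.2.2.
- **Windows.** A reader might infer from the shared Visit 5 and termination column that two sessions must collide. That column is a heading in a procedures schedule. The rule acts on analysis windows that are not yet set. Treatment does go on after Week 26 ("Subjects will continue to receive treatment for the length of the trial"), so a later ECG is possible, but a collision needs an assumed window. The ECG is also exempt from routine termination procedures.
- **Comparison with PCS counts.** The rule using all assessments governs the overall PCS table. The by-visit vital-sign and laboratory summaries state no worst-in-window rule either, so the contrast holds only at the overall level.
- **Controls.** Table shells (SAP 6) and independent quality control (SAP 7) may settle the handling. The shells are not in the supplied text, so this cannot be judged either way.
- **Safeguards.** ECG results remain in the listings, and clinically significant ECG changes are reported as adverse events (Protocol 11.4.4).

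None of this removes the core problem: a stated rule, without exception, defeats the stated purpose of these tables. Quality control would check that a program follows the SAP, not that the SAP's two rules fit together.

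**Conclusion.** The point holds as a minor correction. As written, the averaging and latest-value rules leave one value per window, so the maximum and greatest-change displays select nothing. Where a window holds a repeat, unscheduled or termination ECG, the rule can only understate the number of subjects above a threshold.

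The effect is probably small: fewer than one subject expected above 450 ms in most assumed scenarios, far less at 480 and 500 ms, and none if no window holds two sessions. This rests entirely on assumed QTc parameters, an assumed share of termination ECGs and an assumed window, because the documents give none of these. A reader might infer that QTc signals would be lost to safety review. The documents do not support that, since the values stay listed and clinically significant changes become adverse events. What is at risk is the accuracy of a descriptive summary table.

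**What to change.** Change SAP 6.3.4 in three ways:

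1. Limit the latest-value rule to the by-visit descriptive statistics, which fits the purpose of windows given in SAP 4.2.1.
2. Base the maximum-QTc and greatest-change categories on the highest triplicate mean among all post-baseline ECG sessions in the window, including unscheduled and Premature Termination ECGs.
3. Add one any-time post-baseline count to the ECG table, to match the overall PCS counts. It also captures a late termination ECG whichever window it is given.

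The cost is a few sentences of SAP text and minor programming, with no new data. The drawback is that taking the highest of several sessions lets in some chance highs, so counts may rise slightly. Showing the number of sessions per window beside the table would let a reader judge this.

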6.3.5 Physical and Neurological Examinations

Physical and neurological exminations will be performed at screening (visit 1) and week 26 (visit 5). Normal and abnormal physical and neurological exam results will be summarized by visit, using counts and percentages. Physical and neurological examination findings will be listed. These will be reviewed for any emergent abnormalities that could be attributed to the new dosage form.

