## 8.2. Inclusion Criteria

Subjects are required to give written consent to participate in the trial. They will be informed that their primary medical practitioner and physiotherapist may be contacted to inform them of the trial and its conditions. Subjects must meet all entry criteria listed below.

- 1. Willingness to participate and give written informed consent
- Men and women ≥ 18 years of age
- 3. Sexually active women who are of child bearing potential will practice an acceptable method of birth control for the duration of the trial as judged by the investigator. Examples of acceptable contraception are: condoms, foams, jellies, diaphragm, intrauterine device, oral or long acting injected contraceptives, bilateral tubal ligation, bilateral oophorectomy, hysterectomy, or having a partner who is incapable of initiating conception. The practice of contraception must have started at least 3 months prior to trial entry.
- 4. If female, negative pregnancy test result at Screening
- 5. Diagnosed with MS and a known history of spasticity
- 6. Completed the double-blind randomized withdrawal phase (Part 3) of trial CLR\_09\_21 with no major protocol violation

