## 11.4.5. Physical and Neurological Examinations; Physical Therapy Assessments

Complete physical and neurological examinations are to be performed at Visit 1 (Week -2), Visit 5 (Week 26), and the Premature Termination Visit (as needed during the Premature Termination visit to follow the resolution of any adverse events).

The complete physical examination will consist of evaluation of the skin, head, eyes, ears, nose, throat, neck, thyroid, lungs, heart, lymph nodes, abdomen, and extremities. Brief, targeted physical examinations are to be performed at other visits as necessary in response to clinically significant AEs.

The neurological examination is to consist of an evaluation of mental status; corneal reflexes; extra-ocular movements; facial sensation (light touch); facial strength; palatal movement; tongue movements; neck extension; neck flexion; head turning; respiration; forced vital capacity; tendon reflexes of the right and left biceps, triceps, supinator, quadriceps, and ankle (scored as 0=absent, 1=reduced, 2=normal, 3=increased, 4=clonus); and plantar stimulation (scored as 0=no movement or flexor; 1=extensor).

Concurrent physical therapy will be assessed at every visit.

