#### 12.3.3.5. Physical and Neurological Examinations

Descriptive statistics will be provided, by treatment group, for proportions of subjects with abnormalities on physical and neurological examinations. Physical and neurological examination findings will be listed. These will be reviewed for any emergent abnormalities that could be attributed to the new dosage form.

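### Normal/abnormal counts by visit will not show change within neurological items already abnormal at Visit 1; paired shift tables should be added

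*SAP*

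**What the plan says.** SAP 6.3.5 places the examinations at Visit 1 and Visit 5 (Week 26) and gives one summary: "Normal and abnormal physical and neurological exam results will be summarized by visit, using counts and percentages". It adds that "Physical and neurological examination findings will be listed". Protocol 12.3.3.5 is no more detailed: "Descriptive statistics will be provided, by treatment group, for proportions of subjects with abnormalities on physical and neurological examinations". It then gives the purpose, which the SAP repeats: "These will be reviewed for any emergent abnormalities that could be attributed to the new dosage form". Neither document defines an emergent abnormality.

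The data collected are richer. Under Protocol 11.4.5, tendon reflexes at five sites on each side are "scored as 0=absent, 1=reduced, 2=normal, 3=increased, 4=clonus", plantar response is scored 0/1, and about a dozen other neurological items are examined. Protocol 8.2 requires subjects to be "Diagnosed with MS and a known history of spasticity".

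The output list in SAP Appendix 2 has Tables 14.1.6 and 14.1.7 (physical and neurological results) and Listings 16.2.11 and 16.2.12. It has no shift table for either examination.

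**The concern.** An emergent abnormality is a within-subject idea: something present at Week 26 that was absent or milder at entry. The planned summary is two cross-sections of a two-level flag. Protocol 5.1 describes spasticity as an abnormal increase in stretch reflexes, so reflexes and plantar response are the items most likely to be abnormal at entry. They are also the items for which the protocol collects scores.

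Both ends of the reflex scale are abnormal, so a subject can move from clonus to absent reflexes and be counted the same way twice. Physical and neurological examinations are named endpoints (Protocol 7.2, SAP 4.1). If the tables cannot register this kind of change, a stable percentage could be read as reassurance that the data were never arranged to give.

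**Working it through.** The plan states no figure here, so there is nothing to reproduce. The check has three parts.

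**1. What the flag does to the reflex scale.** This assumes that any grade other than 2, the grade labelled normal, is classed as abnormal.

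| Visit 1 to Visit 5 | Flag | Effect on the by-visit count |
|---|---|---|
| 2 to 3 | normal to abnormal | adds one |
| 3 to 4 | abnormal to abnormal | none |
| 4 to 0 | abnormal to abnormal | none |

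The last two rows follow from dichotomising alone. No baseline rate is needed.

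**2. How much could be hidden.** Let N be subjects examined at both visits, p the share already abnormal at Visit 1 on the flag being tabulated, and w the share who truly worsen, independent of entry status.

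- Worsenings that can appear: N(1 − p)w
- Worsenings that stay within abnormal: Npw, which is a fraction p of the total whatever w is
- Week 26 percentage abnormal if nobody improves: p + (1 − p)w

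N = 250 is the Week 26 target in the protocol and SAP. Both p and w are assumptions. With w = 5% there are 250 × 0.05 = 12.5 worsenings:

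| p | Can appear | Hidden | Week 26 % abnormal |
|---|---|---|---|
| 5% | 11.875 | 0.625 | 9.75 |
| 50% | 6.25 | 6.25 | 52.50 |
| 80% | 2.50 | 10.00 | 81.00 |
| 90% | 1.25 | 11.25 | 90.50 |
| 95% | 0.625 | 11.875 | 95.25 |

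At p = 90%, the worsenings that can appear are 0.5 of 5 for w = 2% and 2.5 of 25 for w = 10%. Separate counts also net improvement against worsening. At p = 90% and w = 5%, an abnormal-to-normal rate of 1.25/225 = 0.56% cancels the visible rise.

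**3. Different subjects at the two visits.** SAP 6 bases percentages on subjects with non-missing data. Footnote b of Protocol Table 1, and Protocol 10.5 and 11.4.5, make these examinations at premature termination as-needed, to follow adverse events. Protocol 9.6.1 asks for end-of-trial assessments as far as possible in leavers, but the specific provisions exempt these. For illustration, take 350 enrolled (Protocol 12.1), 90% abnormal at entry (315 abnormal, 35 normal), 100 leavers not re-examined, and no subject changing:

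- All leavers abnormal: (315 − 100)/250 = 215/250 = 86%
- Leavers proportional (90 abnormal, 10 normal): 225/250 = 90%
- All 35 normal subjects among the leavers, with 65 abnormal: 250/250 = 100%

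The first and third are extremes. They bound what dropout alone can do to the Week 26 figure.

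Elsewhere the SAP handles this. Sections 6.3.2 to 6.3.4 give change from Visit 1 for vital signs, laboratory tests and ECG, with baseline statistics for the subjects who have change data. Section 6.3.3 adds Visit 1 to Visit 5 laboratory shift tables. Dosing also has a shift table (14.1.8.1.3). Section 6.3.5 has no paired comparison.

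**The case against.** The strongest reply is that the table is not the only safeguard. Findings are listed by subject and reviewed. Protocol 11.4.1.2 sends clinically significant change in a pre-existing condition to the AE page. Protocol 12.3.3.1 counts increased severity or frequency of such a condition as an AE, and SAP 6.3.1 tabulates TEAEs in detail. This stands. A reader might infer that emergent abnormalities cannot show at all, or that the listing review is the only route left. The documents support neither. The AE route does depend on the investigator's judgment of significance, and the listing review has no stated criterion.

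Second, Table 14.1.7 may be by item. The text does not say and the shell is not in the documents. If it is by item, a subject with abnormal reflexes can still be counted as newly abnormal on mental status, and items rarely abnormal at entry lose little (the 5% row above). The problem then narrows to items commonly abnormal at entry. SAP 6 also gives counts per category for categorical data in general, so a display of the 0–4 grades by visit is not excluded. That would still be unpaired.

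Third, the entry rate is inferred. Eligibility requires only a history of spasticity, and subjects rolling over from CLR_09_21 may already be on treatment at Visit 1. This is why a range is shown.

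**Conclusion.** The point holds as a gap in the planned summary. Change within an item already abnormal at Visit 1 does not appear in normal/abnormal counts, and the difference between visits mixes within-subject change with dropout. The hidden share of worsening equals the share abnormal at entry: half at 50%, nine-tenths at 90%. This assumes that worsening is independent of entry status. The documents give neither rate.

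A reader might go further and infer that dropout would leave the two visits showing the same percentage while real change occurs. That needs an extreme case. If all 100 leavers were abnormal and 10 of the 35 normal subjects converted (10/35 = 28.6%), Week 26 shows (215 + 10)/250 = 90%, the same as entry. With proportional dropout, 25 normal subjects remain, 25 × 0.286 = 7.1 convert, and the figure is (225 + 7.1)/250 = 92.9%, a visible rise. The documents do not support the extreme case.

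The study is descriptive and the item-level data are collected and listed. No sample size, alpha or power is affected, and nothing is irrecoverable. The change is still worth making, because the planned summary does not match the stated aim.

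**What to change.** Keep the by-visit counts, since Protocol 12.3.3.5 specifies proportions with abnormalities. Add to SAP 6.3.5 and Appendix 2 shift tables from Visit 1 to Visit 5 in subjects with both examinations, overall and by Safety Group:

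- Tendon reflexes: the 0–4 grades, by site and side.
- Plantar response: the 0/1 score.
- Other neurological items and physical examination body systems: normal/abnormal.

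Report the number of subjects with any item newly abnormal. For reflexes, report shifts toward increased or clonus separately from shifts toward reduced or absent. A single count of worsening by one or more grades has no direction on a scale where the middle grade is normal. State in 6.3.5 what counts as emergent for the listing review, and whether Tables 14.1.6 and 14.1.7 are by item.

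The cost is SAP wording and a modest set of descriptive tables from data already collected. With ten reflex sites, the plantar response, the other neurological items and the body systems, this is more than one or two tables, but it needs no new assessments.
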